6.0 DOSE DELAYS/DOSE MODIFICATIONS (ARM B)

The following algorithms are meant as guidelines only; adjustments to chemotherapy may be made at the discretion of the treating physician.

Renal Dysfunction:

CrCl 10 to 50 ml/min: administer 75% of etoposide dose

CrCl <10ml/min: administer 50% of etoposide dose

Congestive heart failure:

Given the low dose and short duration of doxorubicin treatment, we do not anticipate significant cardiac toxicity. However, if a prolongation of the QTc interval (>0.48 sec), a decrease in ejection fraction to <50%, or a decrease in left ventricular shortening fraction to <27%, doxorubicin should be omitted one week, any existing electrolyte or micronutrient deficiencies corrected, and the tests repeated. If the abnormalities persist, doxorubicin treatment should be permanently discontinued. Missed doses due to cardiac toxicity will not be made up.

Hematologic abnormalities:

Hold etoposide for ANC <500/mcl or platelet < 50 K/cumm. May restart when ANC ≥ 1000/mcl and platelet > 100 K/cumm. Etoposide may be restarted at full dose or reduced dose at the discretion of the treating physician. Missed doses will not be made up.

Baseline Permissible ANC	Subsequent ANC	Growth Factor Support, Treatment Delay and Follow-up Labs	Dose Reduction of Doxorubicin Based on Rates of Abnormal Lab Recovery
ANC ≥ 1000/mcl	ANC ≥ 1000/mcl	None	None
	ANC < 1000/mcl but > 500/mcl	G-CSF 5 mcg/kg SQ or IV qday x up to 5 days. Check CBC daily. When ANC ≥ 1000/mcl, restart treatment.	None if ANC recovers to ≥ 1000/mcl within 5 doses of G-CSF.
			Decrease to 20 mg/m ² if ANC recovers to ≥ 1000/mcl after 5 doses of G-CSF.
			Decrease to 15 mg/m ² if ANC takes > 14 days to become permissible.
	ANC < 500/mcl	G-CSF 5 mcg/kg SQ or IV qday x up to 5 days. Check CBC daily. When ANC ≥ 1000/mcl, restart treatment.	Decrease to 20 mg/m ² if ANC recovers to ≥ 1000/mcl within 5 doses of G-CSF.
			Decrease to 15 mg/m ² if ANC recovers to ≥ 1000/mcl after 5 doses of G-CSF.
Discontinue treatment if ANC takes > 21 days to become permissible.			

Baseline Permissible Platelets	Subsequent Platelet count	Treatment Delay and Follow-up lab§	Dose Reduction of Doxorubicin Based on Rates of Abnormal Lab Recovery
Platelet \geq 100 K/cumm	Plt \geq 50 K/cumm	None	None
	Plt $<$ 50 K/cumm but \geq 10 K/cumm	Hold treatment. Check CBC twice a week. When plt \geq 50 K/cumm, restart treatment. Transfuse as needed to keep plt \geq 20 K/cumm	Decrease to 20 mg/m ² if plt recovers to \geq 50 K/cumm within 7 days.
			Decrease to 15 mg/m ² if plt recovers to \geq 50 K/cumm within 21 days.
	Plt \leq 10 K/cumm	Hold treatment. Check CBC twice a week. Transfuse as needed to keep plt \geq 20,000. When plt \geq 100 K/cumm without transfusion, restart treatment.	Decrease to 15 mg/m ² if plt recovers to \geq 50 K/cumm within 21 days.
Discontinue treatment if plt takes $>$ 21 days to recover to \geq 50 K/cumm			

§ All follow-up labs for dose modifications are +/- 3 days.

Hyperbilirubinemia:

Direct Bilirubin:	2 – 2.99 mg/dL	Reduce etoposide and doxorubicin dose by 50%
	3 – 4.99 mg/dL	Reduce etoposide and doxorubicin dose by 75%
	\geq 5 mg/dL	Hold etoposide and doxorubicin

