3.2 Inclusion Criteria – Arm B

1. Recurrent pediatric brain tumors determined candidates for MLA as determined by the treating neurosurgeon.
2. Unequivocal evidence of tumor progression by MRI (see Section 12).
3. There must be an interval of at least 12 weeks from the completion of radiotherapy to study registration except if there is unequivocal evidence for tumor recurrence per RANO criteria (see Section 12). When the interval is less than 12 weeks from the completion of radiotherapy, the use of PET scan is allowed to differentiate between evidence of tumor recurrence and pseudoprogression.
4. Recurrent lesions with dimension and contour that are determined by the treating neurosurgeon to be appropriate for MLA.
5. Age 3 to \leq 21
6. Karnofsky/Lansky performance status \geq 60%, see Appendix 1.
7. Adequate cardiac function as determined by a shortening fraction \geq 27% or left ventricular ejection fraction \geq 50% by echocardiogram within the past 1 year prior to registration.
8. Prior anthracycline therapy does not exceed 200 mg/m² total cumulative dose.
9. Adequate bone marrow and hepatic function as defined below (must be within 7 days of MLA):
 - a. Absolute neutrophil count (ANC) \geq 1000/mcl (G-CSF is allowed)
 - b. Platelets \geq 100 K/cumm
 - c. Hemoglobin \geq 9 g/dL (pRBC transfusion +/- ESA are allowed)
 - d. ALT \leq 3 x ULN

- e. $AST \leq 3 \times ULN$
 - f. $ALP \leq 3 \times ULN$. If ALP is $> 3 \times ULN$, GGT must be checked and be $\leq 3 \times ULN$.
 - g. $Bilirubin \leq 2 \times ULN$
10. At the time of registration, patient must have recovered from the toxic effects of prior therapy to no more than grade 1 toxicity.
 11. At the time of registration, patient must be at least 4 weeks from other prior cytotoxic chemotherapy.
 12. Women of childbearing potential and men must agree to use adequate contraception (hormonal or barrier method of birth control, abstinence) prior to study entry and for the duration of study participation. Should a woman become pregnant or suspect she is pregnant while participating in this study, she must inform her treating physician immediately.
 13. Ability to understand and willingness to sign an IRB approved written informed consent document (or that of legally authorized representative, if applicable).

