5.4 Agent Administration

Arm B only: Doxorubicin will be given intravenously on an outpatient basis weekly for 6 weeks at a dose of 25 mg/m² over 5-30 minutes. Doxorubicin will be held for an ANC of <500/mcl or platelets <50 K/cumm. Following the 6 weeks of doxorubicin, etoposide at 50 mg/m²/day will be given orally for 21 days of each 28-day cycle to begin once ANC ≥ 1000/mcl and platelets ≥ 100 K/cumm. Etoposide will be held for ANC of < 500/mcl or platelets < 50 K/cumm. Patients may receive up to 24 cycles of etoposide.

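### In the Section 6.0 platelet table, the 10–50 K row does not require its 50 K restart count to be untransfused, and a count of exactly 10 K falls in two rows

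*Combined protocol and SAP*

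**What the plan says.** All of this concerns doxorubicin in Arm B.

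- Section 6.0, platelet table, middle row (below 50 K, down to and including 10 K): hold, check the CBC twice a week, and on reaching "50 K/cumm, restart treatment. Transfuse as needed to keep plt" at 20 K or more. The dose is then 20 mg/m² if 50 K is regained within 7 days, or 15 mg/m² if within 21 days.
- Same table, lowest row (10 K or less): hold, same CBC schedule, same 20 K transfusion floor. The restart count here is 100 "K/cumm without transfusion, restart treatment". The dose is 15 mg/m² if 50 K is regained within 21 days.
- Same table, stop line: "Discontinue treatment if plt takes" more than 21 days to get back to 50 K.
- Section 5.4: "Doxorubicin will be held for an ANC of <500/mcl or platelets <50 K/cumm". It says nothing about transfusion.
- Section 3.2 states which support may lie behind a qualifying laboratory value. Growth factor is allowed for ANC, and for hemoglobin "pRBC transfusion +/- ESA are allowed". The platelet line is silent.
- Section 6.0 opens by calling its algorithms guidelines and adds that "adjustments to chemotherapy may be made at the discretion of the treating physician".

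**The concern.** A platelet count taken soon after a transfusion does not show that the child's own marrow has recovered. Two adjacent cells both direct transfusion, but only one requires an untransfused restart count. A reader applying ordinary drafting logic will conclude that the other does not need it. On that reading, weekly myelosuppressive treatment can resume on a borrowed count. The same count may also be read as rapid recovery, so that the higher of the two reduced doses goes to a child whose marrow is in fact slow.

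The overlap at 10 K is a separate matter. Two people using the table correctly can apply different restart counts, and sometimes different doses, to the same child.

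**Working it through.** No sample size, power or error rate is involved, and the plan states no figure to reproduce. The check is a comparison of the two rows and some short arithmetic.

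**Step 1. The rows side by side (Section 6.0).**

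| | Middle row | Lowest row |
|---|---|---|
| Range | 10 K ≤ count < 50 K | count ≤ 10 K |
| Transfusion floor | 20 K | 20 K |
| Restart count | 50 K, no condition | 100 K, untransfused |
| Dose, 50 K regained within 7 days | 20 mg/m² | 15 mg/m² |
| Dose, 50 K regained on days 8–21 | 15 mg/m² | 15 mg/m² |

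**Step 2. Is the missing condition supplied elsewhere?** Section 5.4 repeats the 50 K threshold without it. Section 3.2 governs entry, not restart. Nothing else in the documents addresses transfusion and doxorubicin restart, and no minimum gap between a transfusion and the recovery count is set.

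**Step 3. Who is affected?** The table directs transfusion only to hold the count at 20 K, so within the middle row it applies at 10–19 K. The rise needed to read 50 K is 50 minus the starting count:

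- from 10 K: 50 − 10 = 40 K
- from 15 K: 50 − 15 = 35 K
- from 19 K: 50 − 19 = 31 K

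The documents give no transfusion increment, so a range has to be assumed. At 10–30 K there is no effect, since even 19 + 30 = 49 K. At 31–39 K only starting counts in the upper part of the band are affected. At 40–50 K every starting count from 10 to 19 K is affected, since 10 + 40 = 50 K.

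**Step 4. Size per dose.** If a transfused 50 K is counted as recovery within 7 days, the dose is 20 rather than 15 mg/m²: 20 / 15 = 1.33, or one third more. If it is counted only for restart, the effect is a dose given while the child's own count is still below 50 K.

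**Step 5. The overlap.** The two ranges share exactly one value, 10 K. At that value the restart count is 50 K or an untransfused 100 K. If 50 K is regained within 7 days, the dose is 20 or 15 mg/m². If it takes 8–21 days, both rows give 15 mg/m² and only the restart count differs.

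**The case against.** There is a good case that this is narrow.

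First, a reader might infer that a transfused 50 K, by the letter of the table, also fixes the dose and escapes the stop line. The text does not support that as a certainty. Only the restart sentence is a bare count. The dose and stop clauses speak of the count recovering, under a column heading about the speed of laboratory recovery, and a transfused value is not naturally called recovery. This objection stands: the dose effect is a possible reading, not the only one. It does not touch the restart sentence.

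Second, Section 3.2 can be turned round. Support is named for ANC and hemoglobin and not for platelets, which suggests that silence means untransfused. That is fair for entry. It does not settle Section 6.0, where the neighbouring row states the condition and this row omits it.

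Third, a reader might go on to total the extra doxorubicin over the six weeks. The documents do not allow this. They say that missed doxorubicin doses are not made up only for cardiac toxicity; the similar hematologic sentence follows the etoposide rules. Whether doses held for platelets are dropped or merely delayed is not stated, and any total depends on it. The weekly CBC in Section 10.2 and the hold in Section 5.4 would also interrupt treatment again if the next count fell below 50 K.

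Fourth, transfusion is directed only to 20 K, Section 1.5 expects the regimen to be well tolerated, and Section 6.0 leaves room for judgement. These limit how often the gap matters. Discretion lets a physician be more cautious, but it does not correct the written default.

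**Conclusion.** Both defects are present in the current text and nothing else in the documents resolves them. In the middle row, a transfused 50 K permits restart as written, and it may also be taken as fast recovery that selects 20 instead of 15 mg/m². At exactly 10 K, two rows give two restart counts and, when recovery is within 7 days, two doses.

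The practical size is small and cannot be put as a rate. The first defect bears mainly on a child transfused at 10–19 K, and only if the rise is at least 31–40 K depending on the starting count; the increment is an assumption and the frequency of such counts is unknown. The second concerns a single value. Section 5.1.2 plans six patients for Arm B. No effect on the efficacy results is claimed. The point is worth taking because a safety rule for children on a weekly anthracycline should not contradict itself, or be looser in one row than in the next through an omitted phrase.

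**What to change.** Two edits to the platelet table:

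1. In the middle row, add *without transfusion* to the 50 K restart count, matching the lowest row, and state that recovery in the dose and stop clauses is read the same way.
2. Change the middle row's lower limit from *≥ 10 K/cumm* to *> 10 K/cumm*, so that exactly 10 K belongs only to the more cautious lowest row.

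The lowest row's own condition stays as it is. Sample size, assessments and analysis do not change. The cost is that a child may occasionally restart later, or stop doxorubicin if the untransfused count takes more than 21 days to reach 50 K. If that child had received only one dose, Section 5.5 would make the child not evaluable for efficacy, which is noticeable in an arm of six but should be rare.

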7.0 REGULATORY AND REPORTING REQUIREMENTS

7.1 Adverse Events (AEs)

Definition: any unfavorable medical occurrence in a human subject including any abnormal sign, symptom, or disease.

Grading: the descriptions and grading scales found in the revised NCI Common Terminology Criteria for Adverse Events (CTCAE) version 4.0 will be utilized for all toxicity reporting. A copy of the CTCAE version 4.0 can be downloaded from the CTEP website.

Attribution (relatedness), Expectedness, and Seriousness: the definitions for the terms listed that should be used are those provided by the Department of Health and Human Services’ Office for Human Research Protections (OHRP). A copy of this guidance can be found on OHRP’s website: <http://www.hhs.gov/ohrp/policy/advevntguid.html>

7.2 Unanticipated Problems

Definition:

- unexpected (in terms of nature, severity, or frequency) given (a) the research procedures that are described in the protocol-related documents, such as the IRB-approved research protocol and informed consent document; and (b) the characteristics of the subject population being studied;
- related or possibly related to participation in the research (“possibly related” means there is a reasonable possibility that the incident, experience, or outcome may have been caused by the procedures involved in the research); and
- suggests that the research places subjects or others at a greater risk of harm (including physical, psychological, economic, or social harm) than was previously known or recognized.

7.3 Noncompliance

Definition: failure to follow any applicable regulation or institutional policies that govern human subjects research or failure to follow the determinations of the IRB. Noncompliance may occur due to lack of knowledge or due to deliberate choice to ignore regulations, institutional policies, or determinations of the IRB.

7.4 Serious Noncompliance

Definition: noncompliance that materially increases risks, that results in substantial harm to subjects or others, or that materially compromises the rights or welfare of participants.

7.5 Protocol Exceptions

Definition: A planned deviation from the approved protocol that are under the research team’s control. Exceptions apply only to a single participant or a singular situation.

Pre-approval of all protocol exceptions must be obtained prior to the event.

7.6 Reporting to the Human Research Protection Office (HRPO) and the Quality Assurance and Safety Monitoring Committee (QASMC) at Washington University

The PI is required to promptly notify the IRB of the following events:

- Any unanticipated problems involving risks to participants or others which occur at WU, any BJH or SLCH institution, or that impacts participants or the conduct of the study.
- Noncompliance with federal regulations or the requirements or determinations of the IRB.

- Receipt of new information that may impact the willingness of participants to participate or continue participation in the research study.

These events must be reported to the IRB within **10 working days** of the occurrence of the event or notification to the PI of the event. The death of a research participant that qualifies as a reportable event should be reported within **1 working day** of the occurrence of the event or notification to the PI of the event.

7.7 Timeframe for Reporting Required Events

Reportable adverse events will be tracked for 30 days following the last day of study treatment for patients in Arm B and for 30 days following the MLA for patients in Arm A. For patients in Arm A, adverse events (of any grade) considered possibly, probably, or definitely related to the MLA need be reported. Adverse events that are possibly, probably, or definitely related to study procedures will be followed until resolution or stabilization of the event. “Stabilization” is defined as remaining at a consistent CTCAE version 4.0 grade of the event for two consecutive assessments. For Arm B, all grade 3 and higher events regardless of attribution are to be reported.

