1.3.1 Prior Clinical Experience with MLA

We have had one of the largest clinical experiences using MLA in the country. To date we have done more than 80 cases, of which approximately two-thirds are high-grade glial neoplasms. In regards to adverse events, patients have experienced transient aphasia, transient hemiparesis, transient hyponatremia, and a documented case of lower extremity deep venous thrombosis. Patients with aphasia or hemiparesis improved over time with steroid therapy. Hyponatremia resolved spontaneously. One patient experienced fatal meningitis. Subsequent in-depth analysis revealed that this patient's meningitis was due to an operating room infrastructure-related contamination and not due to equipment contamination related to performance of the MLA procedure.

1.4 MLA followed by Standard of Care in Newly Diagnosed Glioma Patients (Arm A)

MLA offers an alternative to some patients with tumors that are unresectable. Complete surgical resection of grade I and II gliomas have a >90% overall survival, although complete resection is not always possible due to the location of the tumor. For tumors with less than a complete resection, chemotherapy or radiation therapy is offered for progressive

and/or symptomatic tumors. For high grade gliomas, patients who have a complete resection of the enhancing tumor at time of diagnosis [29, 30] or at relapse have a longer survival compared to those with residual disease [31]. In this arm of the study, patients with any grade glioma who are candidates for MLA will undergo this procedure followed by standard of care treatment.

1.5 MLA followed by Doxorubicin and Etoposide in Relapsed Malignant Tumor Patients (Arm B)

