13.0 DATA AND SAFETY MONITORING

In compliance with the Washington University Institutional Data and Safety Monitoring Plan, the Principal Investigator will provide a Data and Safety Monitoring (DSM) report to the Washington University Quality Assurance and Safety Monitoring Committee (QASMC) semi-annually beginning six months after accrual has opened (if at least five patients have been enrolled) or one year after accrual has opened (if fewer than five patients have been enrolled at the six-month mark).

The Principal Investigator will review all patient data at least every six months, and provide a semi-annual report to the QASMC. This report will include:

- HRPO protocol number, protocol title, Principal Investigator name, data coordinator name, regulatory coordinator name, and statistician
- Date of initial HRPO approval, date of most recent consent HRPO approval/revision, date of HRPO expiration, date of most recent QA audit, study status, and phase of study
- History of study including summary of substantive amendments; summary of accrual suspensions including start/stop dates and reason; and summary of protocol exceptions, error, or breach of confidentiality including start/stop dates and reason

- Study-wide target accrual and study-wide actual accrual
- Protocol activation date
- Average rate of accrual observed in year 1, year 2, and subsequent years
- Expected accrual end date and accrual by arm
- Objectives of protocol with supporting data and list the number of participants who have met each objective
- Measures of efficacy
- Early stopping rules with supporting data and list the number of participants who have met the early stopping rules
- Summary of toxicities separated by arm
- Abstract submissions/publications
- Summary of any recent literature that may affect the safety or ethics of the study

The study principal investigator and Research Patient Coordinator will monitor for serious toxicities on an ongoing basis. Once the principal investigator or Research Patient Coordinator becomes aware of an adverse event, the AE will be reported to the HRPO and QASMC according to institutional guidelines.

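### Section 7.7 filters adverse events differently in two arms that share the same ablation procedure, so any-grade MLA-related toxicity and all-cause grade 3+ toxicity are each fully reportable in only 6 of 12 patients

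*Combined protocol and SAP*

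**What the plan says.** Section 7.7 sets the reporting rule arm by arm. One sentence reads "For patients in Arm A, adverse events (of any grade) considered possibly, probably, or definitely related to the MLA need be reported"; another reads "For Arm B, all grade 3 and higher events regardless of attribution are to be reported". The windows also differ. For Arm B the text is "Reportable adverse events will be tracked for 30 days following the last day of study treatment for patients in Arm B"; Arm A tracking instead stops one month (30 days) after the ablation. A further sentence carries no limit by arm or grade: "Adverse events that are possibly, probably, or definitely related to study procedures will be followed until resolution or stabilization of the event".

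Other sections bear on how this is read:

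- **Sections 5.1.1, 5.1.2 and 5.5.** Six patients enter each arm, all undergo MLA, and all are evaluable for toxicity. In Arm B, doxorubicin starts about 7 days after MLA (range 2-14).
- **Section 7.1.** CTCAE grading and the attribution definitions apply to the whole study.
- **Section 11.** There are two forms. The Adverse Events Form has a time window for each arm but no grade or attribution filter. The AE Reporting Form refers back to Section 7.0.
- **Sections 10.1 and 10.2.** Both calendars start adverse-event assessment at MLA and state no filter.
- **Section 13.** The monitoring report must contain a "Summary of toxicities separated by arm".
- **Section 1.3.1.** In the site's earlier MLA cases, "patients have experienced transient aphasia, transient hemiparesis, transient hyponatremia" are listed among the complications, without CTCAE grades.

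**The concern.** The procedure is common to both arms, so its toxicity is the one safety question on which all 12 patients could contribute. The two filters work on different axes: Arm A selects on cause and Arm B on severity. A grade 1-2 neurological event attributed to MLA must be reported for an Arm A child but not for an Arm B child. A grade 3 or 4 event in the month after MLA that the investigator attributes to tumour must be reported in Arm B but not in Arm A. Completeness of severe-event reporting in Arm A therefore rests on an unblinded judgement of cause.

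Two things are at stake. The monitoring committee will see toxicity by arm built on two different definitions, so a difference between the columns may come from the rule alone. And Section 14 presents the trial as a pilot whose data will inform later studies. For some event classes it would do so from half of an already small sample.

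The point concerns which events count, not how long they are tracked.

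**Working it through.** **No plan figure to reproduce.** Section 14 bases six per arm on feasibility and gives no event rate, power or safety analysis. The total is 6 + 6 = 12 (Sections 5.1.1, 5.1.2 and 14).

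**Step 1. Cross the two filters**, for events within 30 days of MLA. This reads the Arm A sentence as requiring only MLA-related events, and Arm B tracking as starting at MLA, as its calendar shows.

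| Event | Arm A | Arm B | Patients covered |
|---|---|---|---|
| MLA-related, grade 1-2 | required | not required | 6 |
| MLA-related, grade 3+ | required | required | 12 |
| Unrelated to MLA, grade 3+ | not required | required | 6 |
| Unrelated to MLA, grade 1-2 | not required | not required | 0 |

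Any-grade MLA-related toxicity (rows 1 and 2) is complete only in Arm A. All-cause grade 3+ toxicity (rows 2 and 3) is complete only in Arm B. Row 2 is covered in both arms, provided Arm B events are attributed to MLA as distinct from the drugs. Section 7.7 does not explicitly ask for that.

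**Step 2. Precision with 6 against 12 patients, for the two incomplete classes.** With zero events, the exact (Clopper-Pearson) two-sided 95% upper limit is 1 − 0.025^(1/n).

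- n = 6: 1 − 0.025^(1/6) = 45.9%
- n = 12: 1 − 0.025^(1/12) = 26.5%

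**Step 3. Chance of seeing at least one event**, 1 − (1 − p)^n. The documents give no rate, so p is assumed.

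| Assumed p | n = 6 | n = 12 |
|---|---|---|
| 5% | 26.5% | 46.0% |
| 10% | 46.9% | 71.8% |
| 20% | 73.8% | 93.1% |

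For example, at p = 10%: 1 − 0.9^6 = 46.9% and 1 − 0.9^12 = 71.8%.

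**Step 4. Distortion of the by-arm summary.** Suppose the true rate of MLA-related events is the same in both arms and a share s of them is grade 3+. From required reports alone, Arm B shows s times Arm A's rate, and a pooled count captures (6 × 1 + 6 × s)/12 of the events. The share s is assumed.

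| Assumed s | Arm B rate ÷ Arm A rate | Share captured when pooled |
|---|---|---|
| 20% | 0.2 | 60% |
| 40% | 0.4 | 70% |
| 60% | 0.6 | 80% |

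**The case against.** A reader might infer that the two filters are opposites with nothing in common, so that MLA toxicity cannot be estimated on 12 patients at all and half the safety sample is lost for every type of event. The documents do not support this. Grade 3+ MLA-related events, clinically the most important class, are required in both arms, and the proposed change adds no patients for them.

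Four further objections deserve an answer.

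- **Reporting is not collection.** The unfiltered Adverse Events Form, the calendars, and the sentence on following related events to their end may mean that low-grade Arm B events are recorded anyway. This stands as a real uncertainty: it cannot be said as fact that Arm B will appear free of mild MLA toxicity. But none of these places requires such entries, and the follow-up sentence governs how long an event is followed, not which events must be reported.
- **The earlier complications are ungraded.** This stands. Section 1.3.1 calls them transient, which does not mean grade 1-2, so how many would fall below the Arm B threshold is unknown.
- **No planned analysis fails.** Correct: Section 2 has no toxicity objective, and Section 14 has no safety analysis or between-arm safety comparison. The effect is on the descriptive summary in Section 13 and on later use of the data.
- **The arms differ in disease and therapy, so different rules may be deliberate.** That can justify an additional chemotherapy rule in Arm B. It does not explain different rules for the month after a shared procedure.

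**Conclusion.** The concern holds in a limited form. Under Section 7.7 as written, grade 1-2 MLA-related events are required only in Arm A and unrelated grade 3+ events only in Arm B. From the required reports, any-grade MLA-related toxicity and all-cause grade 3+ toxicity are each complete on 6 of 12 patients, and the by-arm summary does not compare like with like.

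For those two classes, covering all 12 patients would lower the zero-event upper limit from 45.9% to 26.5%. At an assumed 10% risk, it would raise the chance of seeing the event at least once from 46.9% to 71.8%. Neither figure applies to severe MLA-related events.

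The conclusion rests on reading 7.7 as the rule that decides what is reported. If the Adverse Events Form is meant to capture every event in both arms, the gap closes in practice, and what remains is to say so in 7.7.

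**What to change.** In Section 7.7, and consistently on the Adverse Events Form, apply one rule to both arms for the 30 days after MLA: report (a) events of any grade at least possibly related to MLA and (b) every grade 3+ event whatever its cause.

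Record attribution to MLA separately from attribution to chemotherapy. Doxorubicin starts 2-14 days after MLA, inside this window, so without separate attribution a pooled MLA rate would mix the two in Arm B. Separate fields reduce that confounding but do not remove it, because attribution remains an unblinded judgement.

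Keep the present Arm B reporting rule after the 30-day window. Tabulate MLA-period events by arm and pooled over 12.

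The cost is a wording change in 7.7 and on the form, a few more low-grade entries in Arm B, and some unrelated severe entries in Arm A. No visit is added and no treatment changes.
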